A meta-analysis exploring the impact of self-directed parenting interventions compared to therapist led parenting interventions for child externalising behaviour found both approaches to be effective in reducing children's behavioural problems with no significant difference between modes of delivery (Tarver et al., 2014). In the context of public services requiring the most cost effective service delivery due to financial constraints (Robertson et al., 2017), self-help interventions can offer a valuable alternative to more resource intensive modes of delivery. Therefore, the focus of this research will be on the self-help delivery of the NHA.

Greater understanding of the effectiveness and mechanisms of the NHA delivered in a self-help format will add to the evidence base around parenting interventions for externalising behavioural problems in children. In turn, this can allow current services to make informed about the most appropriate interventions which is particularly important given the NHA is currently being used in NHS services.

STUDY OBJECTIVES AND PURPOSE

PURPOSE AND PRIMARY OBJECTIVES

The purpose of the study is to increase the evidence base for the NHA parent training programme.

The primary objective of this study is to explore the effectiveness of the Nurtured Heart Approach parent training programme when delivered in a guided self-help format. Therefore, the primary research question is:

When delivered in a guided self-help format, is the NHA effective in reducing parent-reported children's behavioural problems?

SECONDARY OBJECTIVE(S)

The secondary research questions are:

1. When delivered in a guided self-help format, is the NHA effective in:
 - a. reducing negative parenting practices?
 - b. increasing parental reflective functioning?
2. To what extent is the NHA a feasible and acceptable intervention for parents of children with behavioural problems when delivered in a guided self-help format?

OUTCOME MEASURES/ENDPOINTS

PRIMARY OUTCOME MEASURE/ENDPOINT

The primary outcome measure is parent-reported child behavioural problems and will be measured at baseline, throughout the intervention and post-intervention four weeks after the intervention has been concluded.

Primary outcome measure

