Across both sites the referred children of participants will remain on the waiting list, with an allocated lead professional, for the duration of the intervention. Consequently, the services will retain clinical responsibility throughout the intervention. When potential participants are identified by staff from the services, in the first instance the allocated lead professional will establish if parents/carers consent to being contacted for research purposes. If consenting to the contact, the doctoral student will then contact potential participants – see Study Procedure below for full details. Staff from the service will have no further role in the research study. However, notes from the intervention sessions will be uploaded to the record of the referred child for each service meaning staff can access session notes if they have a legitimate reason to do so. This will be made clear to participants at the outset of the study.

SELECTION OF PARTICIPANTS

ELIGIBILITY CRITERIA

Participants will be parents/carers of children who have been referred to NHS children's services for behavioural problems. Participants will be recruited from waiting lists of NHS children's services as outlined above.

Inclusion Criteria

- The referred child is aged between three and eleven years old.
- The referred child is on a waiting list for an NHS children's service in the primary or secondary study site.

- The referred child's behavioural problems are one of the primary reasons for referral to the NHS service.
- The parent/carer identifies the referred child's behaviour as problematic.

NICE guidelines only recommend parent-focused interventions for behavioural problems with children aged between 3 and 11 years old (NICE, 2017). Child behavioural problems are an important focus of this research, hence the requirement for the referred child's behaviour to be one of the primary reasons for referral. The requirement for children to be on a waiting list for an NHS children's service means that the child and parent will be able to access treatment as usual regardless of this research and will retain an allocated lead professional from the service though the intervention. Finally, the parent/carer needs to identify the behaviour as problematic; otherwise, a guided self-help intervention would not be appropriate.

Exclusion Criteria

- The referred child has a diagnosis of developmental delay or learning disability.

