- The family is current receiving active multi-agency involvement (e.g. social care, police or youth offending in addition to NHS services).
- The parent/carer is aged under 18.
- The parent/carer is unable to read or speak English fluently.

Crnic et al. (2004) state the function of behavioural problems is often different for children with a developmental delay or learning disability, making the NHA potentially unsuitable. Similarly, multi-agency involvement and parents aged under 18 years old (legally children themselves) indicate a level of need beyond what would be appropriate for a self-help intervention. The language requirement is necessary for the participants to be able to read the self-help chapters and partake in the guided self-help conversations.

Sampling

The study aims to recruit six participants and convenience sampling will be used to identify the participants.

Size of sample

Single case designs typically have between three and six participants; consensus indicates three cases is the minimum to demonstrate an experimental effect (Kratochwill et al., 2010), while more than six participants is unlikely to be feasible given the amount of data that is required from each participant in single case design research (Barlow et al., 2009)

This study aims to recruit six participants. If successful, this maximises the power of the design without compromising feasibility. If recruitment proves challenging, there is capacity to reduce numbers to three participants without invalidating the findings. Participants will be replaced if drop-out occurs during the baseline phase.

Sampling technique

Convenience sampling will be used to select the participants. Staff working in the specific services will be aware of the eligibility criteria for the study and will identify potential participants. If there are more than six parents/carers willing to participate, participants will be contacted in the chronological order by which they were identified by staff.

This will not result in a representative sample. However, this is not a problem in single case research designs (Barlow et al., 2009), as the small number of participants renders the sample unrepresentative regardless of the sampling technique. The strength of the design comes instead from the systematic and repeated measurement of specific variables (Barlow et al., 2009).

RECRUITMENT

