Potential participants will be given a minimum of 24 hours to consider their participation before they are contacted by a member of their usual care team to give their verbal consent. If they subsequently decide to take part, the doctoral student will contact them (contact details will be passed on by the clinician who made the initial contact with the participants permission) and will be asked to sign an Informed Consent Form (ICF). The member of the usual care team who made the initial approach will also be asked to record in the referred child's clinical notes that verbal consent has been obtained for their parent/carer's contact details to be passed on to the research team. Participants will be able to sign the ICF electronically or can sign, scan and send back the form electronically. It will be explained to the potential participants that participation in the research study will not impact the treatment as usual that they receive from the service for which the referred child is on a waiting list.

It will be explained to the potential participant that entry into the trial is entirely voluntary and that their treatment and care will not be affected by their decision. It will also be explained that they can withdraw at any time, but attempts will be made to avoid this occurrence. In the event of their withdrawal, it will be explained that their data collected so far may not be erased in accordance with the University's Research Privacy Notice and information given in the Participant Information Sheet and we will seek consent to use the data in the final analyses where appropriate.

Participant Payment

Participants will not be paid to participate in the trial. There is evidence to suggest that providing a financial incentive may reduce overall intrinsic motivation to participate in research (Zutlevics, 2016). Intrinsic motivation will be important for participants' desire to learn and attempt new parenting strategies and consequently, anything that may threaten this could impact the validity of the study. Therefore, no payment will be made to participants. Participants will not incur any additional costs as a result of participating in the research.

Through participating in the intervention, participants will receive the book "Transforming the Intense Child Workbook" (Glasser, 2016) in six parts and will keep their workbook on completion of the intervention.

CONSENT

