The participant no longer meets the eligibility criteria for the study. The researcher informs them and the participant is withdrawn from the study.

The participant completes the intervention phase and continues to the follow-up phase.

Follow-up Phase

The researcher will contact the participants to complete the questionnaires for the last time and arrange a follow-up interview with an independent researcher. The follow-up interview is the participant's chance to give feedback on the intervention and how you found it.

The participant decides they do not want to continue taking part in the study and informs the researcher.

After taking part in the interview, the participant has completed the study and will be sent an overview of the research unless they have opted out.

STUDY REGIMEN

The screening procedure is outlined above in the eligibility, recruitment and consent sections.

Baseline phase

Following informed consent, participants will begin the baseline phase. During the baseline phase, participants will be contacted twice a week by phone by the doctoral student to collect the data. The table below shows the frequency of administration for each measure throughout the study. The exact timing of phone calls will be organised with each participant around their availability and the availability of the doctoral student.

The necessity to complete multiple measures will be made clear to participants both in the initial conversation and PIS. If participants do not consistently complete the measures, the researcher will speak to the participant to identify why and explain the impact on the research. If measures continue not to be completed during the baseline phase, participants may be withdrawn from the study.

If stability is not achieved on any variable, participant data will be considered on a case-by-case basis. Lack of stability likely to undermine the validity of subsequent results may result in participants being withdrawn from the study. However, because each participant acts as their own control, a limited amount of variability may not have a significant impact on the study (Kratochwill et al., 2010).

Intervention phase

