Multidimensional Assessment of Parenting Scale (MAPS)	✓	✓	✓	✓	✓	✓		✓		✓		✓		✓		✓		✓	✓
Parental Reflective Functioning Questionnaire (PRFQ)	✓	✓	✓	✓	✓	✓		✓		✓		✓		✓		✓		✓	✓
Brief Problem Monitor (BPM)	✓	✓	✓	✓	✓	✓		✓		✓		✓		✓		✓		✓	✓

SCHEDULE OF PROCEDURES

Procedures	Sessions			
	Screening	Baseline (weeks 1-3)	Intervention (weeks 4-9)	Follow up (week 13)
Informed consent	x			
Demographics		x		
Measure collection		x	x	x
Intervention			x	
Change interview				x

WITHDRAWAL

Participants may be withdrawn from the trial either at their own request or at the discretion of the investigator (with input from the whole research team). The participants will be made aware that this will not affect their future care. Participants will be made aware (via the information sheet and consent form) that should they withdraw the data collected to date may not be erased in accordance with the University's Research Privacy Notice and information given in the Participant Information Sheet and may still be used in the final analysis.

Participants who withdraw prior to starting the intervention will be replaced. After starting the intervention phase, replacement of participants will be considered on a case-by-case basis depending on individual circumstances. If a participant withdraws before the start of the intervention phase, they will not receive the self-help workbook, but will be made aware that they can purchase the book themselves.

ETHICAL AND REGULATORY CONSIDERATIONS

ASSESSMENT AND MANAGEMENT OF RISK

If information is disclosed during the study that could pose a risk of harm to the participant or others, the researcher will discuss this with the CI and where appropriate report accordingly.

Risks will be managed in accordance with each trust's safeguarding policy. The Health and Care Professions Council (HCPC) practitioner psychologist guidance will also be adhered to. During participation in the study, the doctoral student may become aware of harm being caused to the referred child or other children. If a disclosure or concerns about a child are raised, the trust policies will be followed and the referred child's usual care team and the chief investigator will be informed at the earliest possible opportunity.

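### The participant flowchart withdraws anyone who stops meeting an entry criterion, two of those criteria can move with the outcome, and no analysis rule covers the shortened series that results

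*Combined protocol and SAP*

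**What the plan says.** All references are to the combined protocol and SAP.

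- **Study Flowchart, Flowchart for Participants.** The baseline and intervention phases each contain the same exit: "The participant no longer meets the eligibility criteria for the study. The researcher informs them and the participant is withdrawn from the study". The follow-up phase has no such exit.
- **Inclusion Criteria.** Among them: "The parent/carer identifies the referred child's behaviour as problematic".
- **Exclusion Criteria.** Among them: "The family is current receiving active multi-agency involvement", with social care and police given as examples.
- **Primary Outcome Measure/Endpoint.** "The primary outcome measure is parent-reported child behavioural problems", taken at baseline, through the intervention and four weeks after it ends.
- **Withdrawal.** Two grounds are named: the participant's wish, or the investigator's judgement with the team's input. Data gathered before withdrawal "may still be used in the final analysis". Once the intervention has begun, replacement is decided individually, with no criteria given.
- **Recruitment.** On withdrawal, "we will seek consent to use the data in the final analyses where appropriate".
- **Data Analysis.** Visual analysis, the Reliable Change Index and clinical significance. Nothing is said about a case whose series stops early.

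**The concern.** An entry criterion normally decides who starts. Here the flowchart also uses the criteria to decide who stays, and two of them can be affected by what the study is measuring.

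The first is the parent's view of the behaviour. It shares both its construct and its informant with the primary outcome. The protocol gives reason to expect that view to shift. Development of the problem cites a parenting-programme study in which parents came to attribute difficulties less to behavioural problems. Interventions reports that the only published study of this approach found parents saw more strengths in their children. A parent who changes their mind in this way could be a success and, on the flowchart's words, ineligible.

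The second is multi-agency involvement. A family whose situation worsens might acquire it. The Adverse Events section says no adverse event data will be collected, so such a case could leave little other trace in the study data.

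At stake is whether the cases with complete series still represent the cases that started. The distortion could run in either direction, depending on who leaves.

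**Working it through.** The protocol states no alpha, power, effect size or dropout rate. The planned six participants rest on single-case convention, so there is no sample-size figure to reproduce. The check is a reading of the rules side by side, a count of what a withdrawn case loses, and an illustration.

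**1. Do the rules agree?** The flowchart makes withdrawal automatic on loss of a criterion. The Withdrawal section does not name that ground and leaves removal to the participant or to the investigator's judgement. The two do not match.

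**2. What does a withdrawn case lose?** The flowchart takes only those who complete the intervention phase into follow-up, so I take collection to stop at withdrawal. From the table of measure frequency in Study Regimen, the BPM has 6 baseline, 6 intervention and 1 follow-up readings: 6 + 6 + 1 = 13 per case. A case withdrawn after session k loses (6 − k) + 1 readings.

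| Withdrawn after session | Readings lost | Readings kept |
|---|---|---|
| 1 | (6 − 1) + 1 = 6 | 7 of 13 |
| 3 | (6 − 3) + 1 = 4 | 9 of 13 |
| 5 | (6 − 5) + 1 = 2 | 11 of 13 |

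The week 13 reading and the change interview are lost every time. PSYCHLOPS and SWEMWBS are scheduled only on the first day of week 1, at the end of week 9 and at week 13. A case withdrawn before the final session therefore has no post-baseline value on either.

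**3. What happens to the readings that exist?** Withdrawal permits their use but does not require it. Recruitment makes use a matter of seeking consent. Data Analysis does not say how a truncated series is graphed, or which reading stands as the end value for reliable change. Exclusion is thus possible but not prescribed.

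**4. Illustration, assuming withdrawn cases are left out and not replaced.** Each case is 1/6 = 17% of the sample. Suppose 3 of 6 improve: 3/6 = 50%.

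- Two who worsened are withdrawn: 3/(6 − 2) = 3/4 = 75%.
- One who improved is withdrawn: (3 − 1)/(6 − 1) = 2/5 = 40%.

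The split is invented. A proportion improved is not a named endpoint; it is simply a count of the planned case-by-case judgements.

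**The case against.** The strongest reply is that the flowcharts are described as written for the participant, so they are a lay summary. The Schedule of Procedures lists no eligibility re-check, and screening is placed in the eligibility, recruitment and consent sections. Inclusion Criteria explains the parent's-view criterion as suitability for guided self-help, and nothing says the question is asked again. This stands as a reason to doubt that the rule would often be triggered. It does not remove the rule, which is unconditional and appears twice.

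A reader might go further and infer any of the following. The documents do not support them.

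- **Success or deterioration in itself removes a case from the results.** Withdrawal and Recruitment both allow for use of data to date. A lower BPM score is not the same as a parent ceasing to see a problem. Worsening behaviour breaches no criterion unless multi-agency involvement follows, and that exclusion has a stated clinical rationale. A parent whose view changes after the last session is kept, because follow-up has no eligibility exit.
- **Children leaving the waiting list are lost too.** The criterion exists ("The referred child is on a waiting list for an NHS children's service in the primary or secondary study site"), but Study Setting says referred children stay on the list while the intervention runs.
- **Losing one improver takes the study below its minimum of three.** Size of sample sets that minimum for cases, not for cases that improve. Losing one from six leaves five.

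Baseline withdrawals cannot reflect an effect of the intervention, and those participants are replaced.

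**Conclusion.** The point holds in a limited form. As written, the flowchart allows exit during the intervention on grounds linked to the parent-reported primary outcome, and it does not match the Withdrawal section. If collection stops at exit, the consequence is a truncated case: 2 to 6 of 13 BPM readings lost for withdrawal after sessions 5 to 1, no week 13 data, no change interview, and no post-baseline PSYCHLOPS or SWEMWBS value. Permissive wording on data use, the absence of a rule for truncated series and open-ended replacement together leave room for such a case to be left out.

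How often this would happen cannot be estimated, because no withdrawal rate is given. The 75% and 40% figures are illustrations that assume exclusion; they are not forecasts. This is worth correcting because each case carries so much of the evidence and the correction is cheap. It is not evidence that the results would be biased.

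**What to change.** 1. State that eligibility is assessed once, before the first baseline reading, and that later loss of a criterion does not by itself end data collection.
2. Where the parent agrees, continue the scheduled readings and the change interview, and mark the event and its date on the case's graph.
3. In Data Analysis, state that every participant who starts the intervention is reported with all available data and the reason for any withdrawal, whether or not replaced.
4. Reconcile the flowchart with the Withdrawal section, and carry the change into the information sheet. Check it also against the Study Regimen text that withdraws participants who do not attend all six sessions, since that rule could end collection by another route.

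Whether the intervention itself continues after such an event is for the clinical team and is not addressed here.

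The cost is a wording change, with no extra participants. Readings that would otherwise have stopped at withdrawal will be collected as already scheduled. The downside is that some retained series will contain a marked co-occurring event, which has to be weighed in the visual analysis.
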